5.1.3. Anticoagulation Consideration

Lenalidomide increases the risk of thrombotic events in patients who are at high risk or with a history a thrombosis, in particular when combined with other drugs known to cause thrombosis. When lenalidomide is combined with other agents such as steroids (e.g. dexamethasone, prednisone), anthracyclines (Doxil, Adriamycin) and erythropoietin the risk of thrombosis is increased.

- All patients receiving lenalidomide should receive prophylactic anti-coagulation. Aspirin (81 or 325 mg) is the recommended agent for anti-coagulation prophylaxis.

Low molecular weight heparin may be utilized in patients that are intolerant to ASA. Coumadin should be used with caution and close monitoring of INR.

- Prophylactic anti-coagulation should be held for platelet counts $< 50,000/\text{mm}^3$ and then restarted when platelet counts are above this level.
- Full therapeutic anti-coagulation should be considered for patients who have a history of venous thromboembolism. Whether therapeutic anti-coagulation is used or not, patients with a history of venous thromboembolism should be closely monitored throughout the study, especially during periods of fluctuating platelet counts.

5.2. General Concomitant Medication and Supportive Care Guidelines

The case report form (CRF) must capture the concurrent use of all other drugs, over-the-counter medications, or alternative therapies including herbal supplements, specifically, St. John's wort.

5.2.1. Concomitant Medications

The use of coumarin-derivative **anticoagulants** such as warfarin (Coumadin®) is not recommended. It may be used for both thrombosis prophylaxis and treatment. However, coumadin should be used with caution and close monitoring of INR. When possible, low molecular weight heparin should be used instead of coumadin.

5.2.2. Supportive Care

- **Nausea/vomiting** Patients with treatment-related nausea should be treated initially with a phenothiazine (prochlorperazine – 10 mg every 8 hours orally as needed or promethazine – 12.5-25 mg IV every 6 hours as needed). If this is inadequate, a benzodiazepine should be added until acute nausea is controlled or toxicity is limiting. Should this prove inadequate acutely, a steroid may be added (*e.g.*, dexamethasone 4 mg every 6 hours as needed). (Steroid use must be limited to 5 consecutive days within a 4 week cycle.)

After acute nausea has resolved, consideration should be given to initiation of prophylactic antiemetic therapy. If nausea recurs despite reasonable medical intervention (as outlined above), dose reduction will be needed as described in Section 6.

- **Diarrhea** should be managed with loperamide: 4 mg at first onset, then 2 mg every 2-4 hours until diarrhea is controlled (maximum = 16 mg loperamide per day).
- **Hand-foot syndrome** may be treated with topical emollients (such as Aquaphor), topical/systemic steroids, and/or antihistamine agents. Vitamin B6 (pyridoxine; 50-150 mg orally each day) may also be used.
- Patients with **neutropenic fever** or infection should be evaluated promptly and treated with IV antibiotic therapy plus/minus therapeutic colony-stimulating factors as appropriate following the ASCO guidelines.²⁴ Packed red blood cell and platelet transfusion should be administered as clinically indicated. GCSF may be used at the discretion of the treating physician.

5.3. Duration of Therapy

In the absence of treatment delays due to adverse event(s), treatment may continue until one of the following criteria applies:

- Disease progression,
- Intercurrent illness that prevents further administration of treatment,

- Unacceptable adverse events(s),
- Patient decides to withdraw from the study, or
- General or specific changes in the patient's condition render the patient unacceptable for further treatment in the judgment of the investigator.

5.4. Duration of Follow Up

Patients removed from study for unacceptable adverse events will be followed until resolution or stabilization of the adverse event. Unless the patient withdraws from the study, the subject will be followed until disease progression or death, whichever comes first.

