1.1.2. Secondary Objectives

- Determine the response rate of cediranib in combination with lenalidomide in patients with iodine refractory, unresectable DTC who have evidence of disease progression within 12 months of study enrollment.
- Determine the toxicity, duration of response, progression free survival, and overall survival in patients with DTC treated with cediranib plus lenalidomide.

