1.3. Secondary Objectives

- Determine response rates and duration of response, early tumor size changes, the toxicity, and overall survival in patients with DTC treated with cediranib or cediranib plus lenalidomide.
- Determine whether the presence of *B-RAF* or *K-RAS* mutations in patients with DTC predict response to cediranib or cediranib plus lenalidomide.

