5.5. Criteria for Removal from Study

Patients will be removed from study when any of the criteria listed in Section 5.3 applies. The reason for study removal and the date the patient was removed will be documented in the Case Report Form.

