- f: Pregnancy tests for females of childbearing potential. A female of childbearing potential (FCBP) is a sexually mature female who: 1) has not undergone a hysterectomy or bilateral oophorectomy; or 2) has not been naturally postmenopausal for at least 24 consecutive months (i.e., has had menses at any time in the preceding 24 consecutive months).
- g: Pregnancy tests must occur within 10 – 14 days and again within 24 hours prior to initiation of lenalidomide. FCBP with regular or no menstruation must have a pregnancy test weekly for the first 28 days and then every 28 days while on therapy (including breaks in therapy); at discontinuation of lenalidomide and at Day 28 post the last dose of lenalidomide. Females with irregular menstruation must have a pregnancy test weekly for the first 28 days and then every 14 days while on therapy (including breaks in therapy), at discontinuation of lenalidomide and at Day 14 and Day 28 post the last dose of lenalidomide (see Appendix H: Lenalidomide Risks of Fetal Exposure, Pregnancy Testing Guidelines and Acceptable Birth Control Methods).
- h: The Lenalidomide Education and Counseling Guidance Document (Appendix I) must be completed and signed by a trained counselor at the participating site prior to each dispensing of lenalidomide treatment. A copy of this document must be maintained in the patient records. The Lenalidomide Information Sheet (Appendix J) will be given to each patient receiving lenalidomide treatment. The patient must read this document prior to starting lenalidomide study treatment and each time they receive a new supply of study drug.
- i: Pre-study, all patients with 1+ protein reading or greater on urinalysis should collect a 24 hour urine collection to measure protein. During the study, patients with 2+ or greater proteinuria should collect a 24 hour urine collection to measure protein. Study medication should be held until 24 hour urine collected and evaluated. See Section 6.2 for dose modification.
- j: Archival tissue should be requested pre-study but should not delay the start of therapy.
- k: Study calendar can vary +/- 3 days without a study violation.
- l: Radiology evaluation repeated every 2 cycles. Subjects on protocol 18 months or more will have radiology evaluation every 4 cycles.
- k: Off-study evaluation.
- m: TSH and thyroglobulin evaluation repeated every 2 cycles.
- n: After 12 months on study, subjects can be evaluated every 2 cycles.

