13.4. Analysis of Secondary Endpoints

13.4.1. Phase I.

The objective response rate of cediranib in combination with lenalidomide in patients with iodine refractory, unresectable DTC who have evidence of disease progression within 6 months of study enrollment will be estimated. In addition, the toxicity, duration of response, progression free survival, and overall survival in patients with DTC treated with cediranib plus lenalidomide will be evaluated.

13.4.2. Phase II.

Overall survival (OS) rates will be estimated and compared between groups using methods similar to that described above for PFS. Response rates will be compared using a chisquare test followed by logistic regression analysis to adjust for covariates.

The percent change in tumor size from baseline to the end of cycle 2 (two months) will be compared between the two groups using a two-sample t test³³. The post-treatment total sum of lengths for a patient with a new lesion will be scored as $1.2 * \max(\text{pre-sum}, \text{post-sum})$ to ensure that the appearance of new lesions corresponds to a disease progression per RECIST criteria. In the event of any early deaths prior to two months, a nonparametric rank sum test will be used in place of the t test, with deaths ranked at the extreme end of the distribution.

Adverse events will be summarized by type and grade. Adverse event rates will be compared between the two treatment groups using a chisquare test for common toxicities and Fisher's exact test for less frequent events.

Repeated measures analysis of variance (RM ANOVA) will be performed to determine the effect of the treatments on serial measurements of TSH and thyroglobulin. It is hypothesized that these levels will decrease over time. Baseline tissue biomarker expression, scored as present or absent, of *B-RAF* and *RAS* mutations will be correlated with response rates using Fisher's exact test, and with PFS and OS by fitting a Cox proportional hazards regression model.

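### Required follow-up stops at progression although overall survival is to be estimated, compared between arms and modelled, so the planned OS results may be biased

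*Combined protocol and SAP*

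**What the plan says.** **Objectives.** Section 1.1.2 lists, for Phase I, "overall survival in patients with DTC treated with cediranib plus lenalidomide". Section 1.3 lists "overall survival in patients with DTC treated with cediranib or cediranib plus lenalidomide".

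**Analysis.** Section 13.4.2 states that "Overall survival (OS) rates will be estimated and compared between groups", with methods like those for PFS. In Section 13.1.2 these are Kaplan-Meier curves, a stratified logrank test and a Cox model. Section 13.4.2 also relates B-RAF and RAS status to outcome, "with PFS and OS by fitting a Cox proportional hazards regression model".

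**Follow-up.** Unless the patient withdraws, Section 5.4 says that "the subject will be followed until disease progression or death, whichever comes first". Section 5.3 states that "treatment may continue until one of the following criteria applies", and disease progression is the first criterion listed. Section 5.5 adds: "Patients will be removed from study when any of the criteria listed in Section 5.3 applies". The last column of the study calendar (Section 10) is the off-study visit, footnoted "k: Off-study evaluation".

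I found no OS definition, OS censoring rule or survival contact after progression.

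**The concern.** The Section 5.4 rule fits PFS as defined in Section 11.1.6, which ends at progression or death. It does not fit OS, because the deaths that separate OS from PFS are those that follow progression.

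If patients leave observation at progression, a Kaplan-Meier or Cox analysis of OS must treat them as censored there. That censoring is informative whenever the risk of death changes at progression. The plan also assumes that the arms progress at different speeds (medians 40 and 70 weeks), so the distortion would differ by arm. If sites record later deaths on their own initiative, ascertainment may vary by site. At stake is a misleading secondary survival result and biomarker association.

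**Working it through.** **1. Can any other provision supply the missing deaths?**

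- Safety reporting (7.4.1, 7.4.2) covers deaths on study and grade 5 events within 30 days of last dose, whatever the attribution. Footnote 2 of 7.4.2 requires a full report even for deaths clearly due to progressive disease. After 30 days, only events at least possibly related to treatment are reportable.
- The 1.5 years of additional follow-up in 13.1.2 belongs to the PFS sample-size calculation and does not extend 5.4.
- Following an adverse event to resolution (5.4) and pregnancy follow-up (7.4) reach only some patients and do not track survival.

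A death from thyroid cancer months after progression therefore has no required route into the data.

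**2. The plan's own PFS figures** (13.1.2: medians 40 and 70 weeks, 36 and 74 patients, one-sided 0.10, 85% power, 1 year accrual, 1.5 years further follow-up)

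- Schoenfeld events: (1.2816 + 1.0364)² / [(36/110)(74/110)(ln 1.75)²] = 5.373/0.06895 = 78, against 80 stated.
- Event probability per arm: 1 − [e^(−λF) − e^(−λ(F+A))]/(λA), with λ = ln 2/median, A = 52.18 and F = 78.27 weeks. This gives 0.830 and 0.640, so 36 × 0.830 + 74 × 0.640 = 29.9 + 47.4 = 77.3 events.

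The design reproduces. It contains no OS input.

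**3. Illustrative OS model.** Two inputs are assumed: the share p of PFS events that are deaths (5–20%) and the median survival M after progression (26–208 weeks). Both are taken as equal in the two arms, and all times as exponential. With μ = ln 2/M, true OS is

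S(t) = e^(−λt) + (1−p)λ[e^(−λt) − e^(−μt)]/(μ−λ).

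For 30-day capture I take last dose as falling at progression and every death in the next 30 days as recorded.

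Deaths by 2.5 years, both arms:

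| p | M (weeks) | Occur | Recorded, 5.4 alone | Recorded with 30-day capture | Missed with capture |
|---|---|---|---|---|---|
| 5% | 26 | 58.6 | 3.9 | 11.7 | 80% |
| 5% | 52 | 43.3 | 3.9 | 7.9 | 82% |
| 5% | 208 | 17.7 | 3.9 | 4.9 | 72% |
| 10% | 52 | 45.1 | 7.7 | 11.5 | 74% |
| 20% | 26 | 61.5 | 15.5 | 22.1 | 64% |
| 20% | 208 | 27.1 | 15.5 | 16.3 | 40% |

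**4. Two-year OS (104 weeks) at p = 10%, M = 52**

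- Cediranib, true: 0.165 + 0.9 × 0.01733 × (0.165 − 0.250)/(0.01333 − 0.01733) = 0.497. Combination, by the same formula: 0.635.
- Kaplan-Meier censored at progression, e^(−pλt): e^(−0.180) = 0.835 and e^(−0.103) = 0.902.
- With 30-day capture the estimated hazard is [pλe^(−λt) + μG(t)]/[e^(−λt) + G(t)], where G(t) is the share alive who progressed within the last 30 days. Integrated to 104 weeks, this gives about 0.77 and 0.86.

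The true difference of about 14 points appears as about 9.

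**5. Direction**

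- Without capture, OS is overstated only if μ > pλ, that is, if M is below the PFS median divided by p. At p = 20% the limits are 40/0.20 = 200 weeks (cediranib) and 70/0.20 = 350 weeks (combination). At 20%/208 weeks, cediranib OS of 0.702 would be shown as 0.697.
- On the hazard-ratio scale that the plan uses, censoring at progression gives 40/70 = 0.57 in every cell, and 30-day capture moves this to about 0.57–0.60. The true OS hazard ratio, by simulation, is about 0.61–0.71.
- The two-year absolute difference shrinks in 9 of the 12 cells (p = 5, 10, 20%; M = 26, 52, 104, 208) and grows in three: 10%/208, 20%/104 and 20%/208.

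**The case against.** **What stands.** Section 5.4 fully serves the primary endpoint. OS has no power target, alpha or decision rule. Section 5.4 does not forbid recording later deaths, and the case report forms were not available, so sites may have collected some. Safety reporting does catch early deaths, which is why the conclusion rests on the counts with 30-day capture. Every OS magnitude depends on inputs that the documents do not give. Section 5.1.2 also stops lenalidomide in Arm B from April 10, 2015, which makes any later OS contrast harder to interpret in any case.

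These points limit the importance of the problem. They do not reconcile 5.4 and 5.5 with 13.4.2, and that conflict needs none of the assumed numbers. The 30-day allowance is also generous: patients who stopped treatment before progressing could have left the window already.

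**Stronger readings that the documents do not support.**

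- A reader might infer that no death after progression would be recorded. Section 7.4 requires some of them to be.
- A reader might infer that the combination's OS benefit would simply be diluted. That holds for the two-year difference in most cells, but the planned logrank and Cox methods work on the hazard scale, where this model overstates the relative benefit.
- A reader might infer that OS must be overstated. The sign depends on M and p.
- A reader might infer that the mutation model would rest mainly on deaths without progression. At 5%/26 weeks with 30-day capture, 11.7 − 3.9 = 7.8 of 11.7 recorded deaths follow progression.

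**Conclusion.** The point holds as a conflict between required data collection and planned analysis. Followed as written, the plan does not systematically collect most deaths after progression, so OS can be biased, usually upward, and the between-arm comparison distorted.

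Under the assumed ranges, with last dose at progression and complete 30-day capture, about 18–62 deaths occur and about 5–22 are recorded (about 40–82% missed). In this model, with survival after progression equal in both arms, the combination's relative OS benefit is overstated. These figures show the possible scale and are not predictions. Confidence is high in the textual conflict and low in any single magnitude. The harm is confined to secondary results, so this should be fixed but does not threaten the primary conclusion.

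**What to change.** Reconcile Sections 5.4, 5.5 and the study calendar with 13.4.2:

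1. For patients already removed, run one vital-status sweep (records or contact, as far as consent allows) before the OS analysis, and report how many remain of unknown status.
2. For patients still followed, collect vital status after progression or end of treatment until death, withdrawal of consent or the final analysis. The same amendment should settle how 5.5, which removes patients from study for any 5.3 reason, fits with 5.4, which keeps following them to progression.
3. Define OS and state that it is censored at the date last known alive.

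If this is not feasible, drop the OS estimate, the between-arm OS comparison and the mutation–OS model.

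The cost is an amendment and modest data-collection work, and the sweep may be incomplete where consent does not cover later contact. Dropping the analyses needs only a text change but gives up a stated secondary objective. The PFS design is unchanged either way.

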5.5. Criteria for Removal from Study

Patients will be removed from study when any of the criteria listed in Section 5.3 applies. The reason for study removal and the date the patient was removed will be documented in the Case Report Form.

6. DOSING DELAYS/DOSE MODIFICATIONS

The dose levels and the general approach to dose modification of cediranib and lenalidomide on this trial are shown below. Managing patients on combination therapy will be discussed below. Adverse events (AEs) should be treated with the appropriate maximum supportive care, and dose reductions should be clearly documented in the case report form (CRF).

The NCI Common Terminology Criteria for Adverse Events (CTCAE) version 5.0 will be utilized for AE reporting.

CTCAE v5.0 documents, including a mapping document, are available on the CTEP website: https://ctep.cancer.gov/protocolDevelopment/electronic_applications/ctc.htm

Dose Level for Phase II study	Cediranib
-2	15 mg cediranib daily
-1	20 mg cediranib daily
0	30 mg cediranib daily

Dose Level for Phase II study	Lenalidomide
-2	Lenalidomide 5 mg on day 1-21 of 28 day cycle
-1	Lenalidomide 10 mg on day 1-21 of 28 day cycle
0	Lenalidomide 15 mg on day 1-21 of 28 day cycle

6.1. Management of Treatment-Emergent Hypertension

Hypertension is more frequently associated with cediranib than lenalidomide. Increases in blood pressure (BP) and cases of hypertension have been associated with many drugs acting on the VEGF pathway. The proposed mechanism for this increase is through inhibition of VEGF-induced peripheral vasodilation. Specific guidelines for management of this adverse event and a table of various antihypertensive medications are provided in Appendix C. In addition, guidance on the collection and recording of BP information is provided in Appendix D.

6.1.1 Management of Hypertension

Adverse event	NCI CTCAE v.5 grade	Management	Cediranib administration
Hypertension	Grade 1 Systolic 120-139 mmHg or diastolic 80-89 mmHg	Consider increased BP monitoring	No change
	Grade 2-Mild Stage 1 hypertension: (140-159 mmHg Systolic or 90-99 mmHg Diasolic)	Start/ add long acting DHP CCB (See Appendix C). Gradually increase dose to control BP up to maximum dose. If partial or no control and still moderate hypertension, see Persistent Moderate Hypertension.	First occurrence: Continue cediranib at full dose or decrease dose by one level Second occurrence: Decrease cediranib dose by one level
	Grade 2-Persistent Moderate Hypertension Stage 1 hypertension: (140-159 mmHg Systolic or 90-99 mmHg Diasolic) Recurrent or persistent \geq 24- 48 hrs);	Start/ add long acting DHP CCB (See Appendix C). Gradually increase dose to control BP up to maximum dose. If partial or no control and still moderate hypertension, add an additional drug and increase dose until BP control up to maximum dose.	Hold cediranib and add additional drugs. Restart cediranib at one lower dose level (when controlled).
	Grade 3 Stage 2 hypertension (systolic \geq 160 mmHg or diastolic \geq 100 mmHg);	If asymptomatic : Hold cediranib and start immediate antihypertensive therapy with 2 drug combination including at least a DHP CCB. Increase dose until BP control up to maximum dose of both agents. If partial or no BP control, add another drug up to 4; increase to optimal or maximal doses on all drugs.	First occurrence: Hold cediranib until blood pressure within Stage 1 hypertension range (systolic 140-159 mmHg or diastolic 90-99 mmHg); and decrease cediranib dose by one level Second occurrence: Hold cediranib until blood pressure within Stage 1

		If symptomatic: stop cediranib, hospitalize with aggressive IV therapy as per hypertensive crisis management	hypertension range (systolic 140-159 mmHg or diastolic 90-99 mmHg); and either decrease cediranib by one dose level or stop cediranib permanently
	Grade 4 Life-threatening consequences (e.g. malignant hypertension, transient or permanent neurological deficit, hypertensive crisis); urgent intervention indicated	Stop cediranib, hospitalize with aggressive IV therapy as per hypertensive crisis management.	Stop cediranib permanently

- While patients are receiving treatment with cediranib, the early initiation of antihypertensive treatment for grade 1 or 2 hypertension to minimize more severe or persistent hypertension is not considered a grade 3 adverse event.
- Decisions to hold or decrease the cediranib dose during treatment must be based on BP readings taken in the clinic by a medical professional.

6.2. Other Hematologic and Non-Hematologic Adverse Events

In the setting of combination therapy, it may be difficult to identify the agent causing the adverse event. When the adverse event could be due to either agent, the dose of lenalidomide should be decreased. When an adverse event is more commonly associated with a particular agent, that drug will be decreased.

Event	AE Grade or Observation	Dose modification (single agent cediranib)	Dose modification (cediranib + lenalidomide)
Neutropenia	Grades 1 and 2	Maintain dose	Maintain dose
	Grade 3	
 • Hold cediranib dose • Follow CBC weekly • Hold cediranib until \leq grade 2, then resume treatment at same dose cediranib or reduce 1 dose level G-CSF may be used for treatment. • Dose reduction should be considered for recurrent episodes. 	
 • Hold cediranib and lenalidomide dose. • Follow CBC weekly. • If neutropenia has resolved to \leq grade 2 prior to the scheduled end of the cycle, restart lenalidomide at next lower dose level and cediranib at the same dose and continue through the scheduled end of the cycle. Otherwise, omit for remainder of cycle and

			
reduce the dose of lenalidomide by 1 dose level at the start of the next cycle. Maintain cediranib dose. Omitted doses are not made up. If neutropenia is the only toxicity for which a dose reduction is required, G-CSF (or other white blood cell growth factor) may be used for treatment and the lenalidomide dose maintained
 
 • Dose reduction should be considered for recurrent episodes.
	Grade 4	
 • Hold cediranib dose • Follow CBC weekly • Hold cediranib until \leq grade 2, then resume treatment at same dose cediranib or reduce 1 dose level • G-CSF may be used for treatment. • Dose reduction should be considered for recurrent episodes. 	
 • Hold cediranib and lenalidomide dose. • Follow CBC weekly. • If neutropenia has resolved to \leq grade 2 prior to the scheduled end of the cycle, restart lenalidomide at next lower dose level and cediranib at the same dose and continue through the scheduled end of the cycle. Otherwise, omit for remainder of cycle and reduce the dose of lenalidomide by 1 dose level at the start of the next cycle. Cediranib dose will be maintained. Omitted doses are not made up. If neutropenia is the only toxicity for which a dose reduction is required, G-CSF (or other white blood cell growth factor) may be used for treatment and the lenalidomide dose maintained. Dose reduction should be considered for recurrent episodes.
Thrombocytopenia	Grades 1 and 2	Maintain Dose	Maintain Dose
	Grade 3	
 • Hold cediranib dose 	
 • Hold cediranib and

		
 • Follow CBC weekly • Hold cediranib until \leq grade 2, then resume treatment at same dose cediranib or reduce 1 dose level • Repeated episodes require dose reduction 	
lenalidomide dose.
 
 • Follow CBC weekly. • Hold prophylactic anti-coagulation for platelet counts \leq 50,000/mm³. Prophylactic anti-coagulation should be resumed when lenalidomide is restarted. • If thrombocytopenia resolves to \leq grade 2 prior to the scheduled end of the cycle, restart lenalidomide at next lower dose level and cediranib at same dose and continue through the scheduled end of the cycle. Otherwise, omit for remainder of cycle and reduce the dose of lenalidomide by 1 dose level at the start of the next cycle. Cediranib dose will remain the same. Omitted doses are not made up.
	Grade 4	
 • Hold cediranib dose. • Follow weekly CBC • Hold cediranib until \leq grade 2, then resume treatment at same dose cediranib or reduce 1 dose level • Repeated episodes require dose reduction 	
 • Hold cediranib and lenalidomide dose. • Follow CBC weekly. • Hold prophylactic anti-coagulation for platelet counts \leq 50,000/mm³. Prophylactic anti-coagulation should be resumed when lenalidomide is restarted. • If thrombocytopenia resolves to \leq grade 2 prior to the scheduled end of the cycle, restart lenalidomide at next lower dose level and cediranib at same dose and continue through the scheduled end of the cycle. Otherwise, omit for remainder of cycle and reduce the dose of lenalidomide by 1 dose level at the start of the next cycle. Cediranib dose will remain the same. Omitted doses are not made up.

Fever, chills, flu-like symptoms	Grades 1-4	Maintain dose	Maintain dose
Fatigue (lethargy, malaise, asthenia)	Grades 1 and 2	Maintain dose. For sustained Grade 2 fatigue, cediranib may be held until \leq grade 1. Then resume same dose.	Maintain dose. For sustained Grade 2 fatigue, cediranib and lenalidomide may be held until \leq grade 1. Then resume same dose or reduce 1 dose level of lenalidomide. If fatigue recurs, cediranib may be reduced 1 dose level. If no further dose reductions are available, the lowest doses of cediranib and lenalidomide may be continued at the discretion of the treating physician.
	Grade 3	Hold cediranib until \leq grade 2, then resume treatment at same dose cediranib or reduce 1 dose level	Hold cediranib and lenalidomide until \leq grade 2, then resume treatment at same dose or reduce 1 dose level of lenalidomide. If fatigue recurs, cediranib may be reduced 1 dose level .
	Grade 4	Hold cediranib until \leq grade 2, then resume treatment at same dose or reduce 1 dose level of cediranib	Hold cediranib and lenalidomide until \leq grade 2, then resume treatment at same dose or reduce 1 dose level of lenalidomide. If fatigue recurs, reduce 1 dose level of cediranib.
Hand-foot syndrome	Grades 1 and 2	Maintain dose	Maintain dose
	Grade 3	Hold cediranib until \leq grade 1, then resume treatment at same dose or reduce 1 dose level of cediranib	Hold cediranib and lenalidomide until \leq grade 1, then resume treatment at same dose or reduce 1 dose level of cediranib
	Grade 4	Hold cediranib until \leq grade 1, then reduce 1 dose level or discontinue treatment	Hold cediranib and lenalidomide until \leq grade 1, then reduce 1 dose level of cediranib or discontinue treatment
AST and/or ALT elevation (SGOT, SGPT)	Grades 1 and 2	Maintain dose	Maintain dose
	Grade 3	Maintain dose. If recurrent, reduce cediranib 1 dose level	Maintain dose. If recurrent, reduce lenalidomide 1 dose level

	Grade 4	Reduce cediranib 1 dose level	Reduce lenalidomide 1 dose level
Proteinuria**	Grade 1	Maintain dose	Maintain dose
	Grade 2	Hold cediranib. Collect 24 hour urine. If 24 hour urine results with \leq Grade 2, continue at same dose.	Hold cediranib and lenalidomide. Collect 24 hour urine. If 24 hour urine results with \leq Grade 2, continue at same dose.
	Grade 3	Hold cediranib. Collect 24 hour urine. If 24 hour urine = Grade 3, hold cediranib until urinalysis \leq grade 2, then reduce 1 dose level of cediranib	Hold cediranib and lenalidomide. Collect 24 hour urine. If 24 hour urine = Grade 3, hold cediranib and lenalidomide until urinalysis \leq grade 2, then reduce 1 dose level of cediranib
	Grade 4 (Nephrotic syndrome)	Discontinue treatment	Discontinue treatment
DVT/ Pulmonary Embolism		Hold cediranib until therapeutic on anti-coagulation. Then resume cediranib at same dose* Discontinue treatment if recurrent DVT/PE when fully anticoagulated.	Hold cediranib and lenalidomide until therapeutic on anti-coagulation. Then resume cediranib and lenalidomide at same dose* Discontinue treatment if recurrent DVT/PE when fully anticoagulated.
Anaphylaxis, Stevens Johnson syndrome, TEN		Discontinue treatment	Discontinue treatment
Bowel perforation		Discontinue treatment	Discontinue treatment
Suspected pregnancy, positive HCG, missed menses		Hold cediranib. If pregnancy ruled out, continue treatment at same dose cediranib.	Hold cediranib and lenalidomide. If pregnancy ruled out, continue treatment at same dose cediranib and lenalidomide
Confirmed pregnancy (endocrine, other fetal exposure to drug)	Grade 4	Discontinue treatment. Appropriate follow-up, see Section 7.3.3.	Discontinue treatment. Appropriate follow-up, see Section 7.3.3.

***Low Molecular Weight Heparin (LMWH) should be first choice for anticoagulation. Coumadin can be used but requires close monitoring of INR. Aspirin can be discontinued in patients who are on therapeutic anticoagulation.**

**** For proteinuria +2 or greater on urinalysis, study drugs should be held and 24 hour urine should be collected to confirm degree of proteinuria. Dose modification based on 24 hour urine protein assessment as above.**

